### **6.5.2. Concomitant Medication**

Concomitant medication will be coded using the WHO drug dictionary (Version March 2017). Concomitant medication will be listed.

### 6.5.3. *Clinical Laboratory Parameters*

All clinical chemistry, haematology, and urinalysis data will be listed. Values for any clinical chemistry, haematology, and urinalysis values outside the reference ranges will be flagged on the individual patient data listings.

Additionally, clinical chemistry, haematology, and urinalysis data outside the reference ranges will be summarized by treatment sequence and age group.

### 6.5.4. *Vital Signs*

Vital signs data will be summarized by treatment and age group, together with changes from baseline, where baseline is defined as predose of Day 1. Furthermore, values for individual patients will be listed.

### 6.5.5. *Blood Glucose Monitoring and Hypoglycemia*

Hypoglycaemic events will be appropriately recorded in the CRF. In the case of a hypoglycaemic event, the actual blood glucose value, if measured, will be recorded in the CRF, together with any treatments administered. Each category of hypoglycaemic events (defined below) will be listed and summarized by treatment and age group for inpatient during the MMTT and inpatient run-in period (Part B only). "During the MMTT" refers to 0 to 300 minutes post the start time of the meal or to the time of the first insulin dose after the MMTT, whichever occurs first. For the inpatient period prior to MMTT, the inpatient period after MMTT (from 300 minutes post the start time of the meal or the time of the first insulin dose after MMTT, whichever occurs first, to the end of inpatient visit), and the outpatient period (between Period 1 and Period 2 or between Period 2 and the follow-up visit), similar summary will be provided by age group independently of randomized treatment assignment. All hypoglycemia occurred during the study will be listed.

Hypoglycemia is defined as follows:

- **Documented Glucose Alert Level (Level 1), PG  $\leq$ 70 mg/dL (3.9 mmol/L):**
  - **Documented symptomatic hypoglycaemia:** an event during which typical symptoms of hypoglycaemia are accompanied by PG  $\leq$ 70 mg/dL (3.9 mmol/L)
  - **Documented asymptomatic hypoglycaemia:** an event not accompanied by typical symptoms of hypoglycaemia but with PG  $\leq$ 70 mg/dL (3.9 mmol/L)
  - **Documented unspecified hypoglycaemia:** an event during which PG  $\leq$ 70 mg/dL (3.9 mmol/L) but no information relative to symptoms of hypoglycaemia was recorded
- **Documented Clinically Significant Hypoglycaemia (Level 2) PG  $<$ 54 mg/dL (3.0 mmol/L):**
  - **Documented symptomatic hypoglycaemia:** an event during which typical symptoms of hypoglycaemia are accompanied by PG  $<$ 54 mg/dL (3.0 mmol/L)
  - **Documented asymptomatic hypoglycaemia:** an event not accompanied by typical symptoms of hypoglycaemia but with PG  $<$ 54 mg/dL (3.0 mmol/L)

- **Documented unspecified hypoglycaemia:** an event during which PG <54 mg/dL (3.0 mmol/L) but no information relative to symptoms of hypoglycaemia was recorded
- **Severe hypoglycaemia (Level 3):** an event requiring assistance of another person to actively administer carbohydrate, glucagon, or other resuscitative actions. During these episodes, the patient has an altered mental status and cannot assist in his/her own care, is semiconscious or unconscious, or experienced coma with or without seizures. Plasma glucose measurements may not be available during such an event, but neurological recovery attributable to the restoration of blood glucose concentration to normal is considered sufficient evidence that the event was induced by a low PG concentration (PG  $\leq$ 70 mg/dL [3.9 mmol/L])
  - **Severe hypoglycaemia in children:** because children have limited ability to detect and/or self-treat hypoglycaemia, severe hypoglycaemia in children is an event in which children have altered mental status, and cannot assist in their care, are semiconscious or unconscious, or in coma with or without convulsions, and may require parenteral therapy (glucagon or IV glucose)
  - **Severe hypoglycaemia requiring medical attention:** a severe hypoglycaemic event when patients require therapy by health care providers (emergency medical teams, emergency room personnel, etc.)
- **Nocturnal hypoglycaemia:** any hypoglycaemic event (documented symptomatic, asymptomatic, probable symptomatic, or severe hypoglycaemia) that occurs at night and presumably during sleep
- **Relative hypoglycaemia:** an event during which typical symptoms of hypoglycaemia, which do not require the assistance of another person, are accompanied by PG >70 mg/dL (3.9 mmol/L), but these levels may be quickly approaching the 70 mg/dL (3.9 mmol/L) threshold
- **Overall (or total) hypoglycaemia:** this optional category combines all cases of hypoglycaemia. If an event of hypoglycaemia falls into multiple subcategories, the event is counted only once in this category
- **Probable symptomatic hypoglycaemia:** an event during which symptoms of hypoglycaemia are not accompanied by a PG measurement but that was presumably caused by a blood glucose concentration  $\leq$ 70 mg/dL (3.9 mmol/L).

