Blood Glucose Sampling (MMTT)				-30, -15, 0 (premeal), 10, 20, 30, 40, 50, 60, 70, 80, 90, 100, 110, 120, 135, 150, 165, 180, 195, 210, 225, 240, 300 minutes (postmeal)		Time is referenced to meal start time. Time 0 is collected immediately prior to start of meal consumption.

Visits	Screening		Study Periods (Periods 1 and 2)		Follow-up ^a /Early Discontinuation ^b	Comments
	102	Telephone Visit	3 and 4		802	
Day	Within 28 days Prior to Day -1	≥ Day -10 ^c	-1 ^d	1	≥14 days After Discharge	
Insulin Lispro PK Sampling				0, 5, 10, 15, 20, 25, 30, 35, 40, 45, 50, 60, 70, 90, 120, 150, 180, 240, 300, 360, and 420 minutes postdose		Sampling times are relative to the time of study drug treatment administration (t = 0) in each period.
Transition to NPH Twice Daily Therapy 7-3 days Prior to Day -1		X				Applicable only to patients using multiple daily injection therapy. Patient can return to pre- study basal insulin following completion of MMTT sampling period per investigator's decision and allowing for transition to NPH prior to next dosing.
Resume Prestudy CSII Rate				X		Applicable only to patients on CSII. CSII with the patient's prestudy insulin will be restarted after completion of assessment period (approximately 420 minutes postdose).
Adverse Events/Hypoglycaemia	X	X	X	X	X	
Concomitant Medications	X	X	X	X	X	

Visits	Screening		Study Periods (Periods 1 and 2)		Follow-up ^a /Early Discontinuation ^b	Comments
	102	Telephone Visit	3 and 4		802	
Day	Within 28 days Prior to Day -1	≥ Day -10 ^c	-1 ^d	1	≥14 days After Discharge	
Patient Discharge from Study Site				X		If the next MMTT (Period 2) is scheduled on the next day, the patient may be discharged after the second MMTT (Period 2).

Abbreviations: BP = blood pressure; CSII = continuous subcutaneous insulin infusion; ECG = electrocardiogram; ED = early discontinuation; IWRS = Interactive Web Response System; MMTT = mixed meal tolerance test; NPH = neutral protamine Hagedorn; PK = pharmacokinetics; SC = subcutaneous.

^a Safety follow-up visit should occur at least 14 days after the completion of Period 2.

^b Early discontinuation procedures will be performed at least 14 days after a patient stops the study after receiving study drug on Day 1 of Period 1 and before Day 1 of Period 2.

^c This is a telephonic visit.

^d In case of dosing on consecutive days, the medical assessments to be conducted on Day -1 of Period 2 may be done on Day 1 of Period 1.

^e Not applicable for patients continuing from Part A.

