5.1.2.1. Inpatient Procedures for Part B

On the day before each MMTT day (i.e., Day -1 in each of the 2 periods if performed on non-consecutive days), patients will arrive at the study site in the early evening (approximately 05:00 PM). Patients on CSII pump will be advised to bring a spare infusion set for the CSII pump when they arrive at the study site. Patients who are not using CCI pump will be switched to a CCI pump during the inpatient procedures. A standardised dinner will be provided where the bolus dose of the patient's usual insulin will be administered via CSII for this meal. Patients on MDI will be started on CCI pump following the evening meal. The pump reservoir will be filled with the study insulin, either LY900014 or Humalog, and a new standard infusion set and catheter will be inserted after a priming dose has been given to test the catheter. In case of immediate infusion set intolerance, a new needle can be inserted up until 12:00 AM (midnight). Following the evening meal, patients will continue their current pump basal rate until the start of the run-in period at which time a fixed low basal rate of 0.1 U/hour will be maintained until 2 hours before the scheduled start time of MMTT. For patients transitioning from MDI therapy, the bolus dose used for the evening meal will be based on their usual insulin to carbohydrate ratio and correction factor if applicable. Additionally, the basal insulin rate for the period between dinner and the start of the overnight infusion should be determined using the 80% of the pre-study total daily NPH dose divided by 24 hours to obtain the hourly basal insulin infusion rate. The new basal rate may be titrated as needed based on the investigator's discretion. Before the start of a run-in period, the cannulation of the vein will be performed. Start of the run-in period will occur following the evening meal (at approximately 09:00 or 10:00 PM). The run-in period will start with a variable IV infusion of glucose (5% dextrose solution) or RHI to reach a target glucose level of 135 ± 25 mg/dL (7.5 ± 1.4 mmol/L). If this target glucose level is not attained before 1100 hours on Day 1, MMTT will be halted and may be performed on a separate visit; an MMTT can only be rescheduled (up to 7 days) once for each study period. During the run-in period, blood glucose concentrations will be monitored at a minimum of 30- to 60-minute intervals.

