## **6.5. Safety and Tolerability Assessments**

### **6.5.1. Adverse Events**

Where changes in severity are recorded in the Case Report Form (CRF), each separate severity of the adverse event (AE) will be reported in the listings, only the most severe will be used in the summary tables. A pre-existing condition is defined as an AE that starts before the patient has provided written informed consent and is ongoing at consent. A nontreatment-emergent AE is defined as an AE that starts after informed consent but prior to dosing (prandial MMTT dosing for Part A and infusion set with study treatment inserted for Part B). A treatment-emergent AE is defined as an AE that occurs postdose or that is present prior to the first dose and becomes more severe postdose.

Treatment-emergent AEs will be summarized by treatment, age group, severity, and relationship to the study drug. The frequency (the number of AEs, the number of patients experiencing an AE, and the percentage of patients experiencing an AE) of treatment-emergent AEs will be summarized by treatment, age group, Medical Dictionary for Regulatory Activities version 20.0 system organ class and preferred term. The summary and frequency AE tables will be presented for all causalities and those considered related to the study drug.

All AEs will be listed. Any serious AEs will be tabulated.

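### In Part B, SAP 6.5.5 pools hypoglycaemia over treatment between study-insulin set insertion and run-in, although SAP 6.5.1 already counts the patient as dosed

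*SAP*

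**What the plan says.** SAP 6.5.5 provides two kinds of hypoglycaemia summary. Events are "listed and summarized by treatment and age group for inpatient during the MMTT and inpatient run-in period (Part B only". The remaining time is introduced with "For the inpatient period prior to MMTT, the inpatient period after MMTT" and extends to the outpatient period; for all of it a "similar summary will be provided by age group independently of randomized treatment assignment". The section also says that every hypoglycaemic event in the study is listed.

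SAP 6.5.1 separates pre-dose from post-dose adverse events. Its reference point is "prandial MMTT dosing for Part A and infusion set with study treatment inserted for Part B".

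Protocol 5.1.2.1 describes the Part B evening. "The pump reservoir will be filled with the study insulin, either LY900014 or Humalog", and a new set and catheter are inserted. The Part B Schedule of Activities (Protocol Section 2) places this change after the Day -1 evening meal. Then "patients will continue their current pump basal rate until the start of the run-in period", which begins at about 21:00 or 22:00, when the rate falls to 0.1 U/hour. Patients from MDI run in that interval at 80% of their total daily NPH dose divided by 24, which the investigator may titrate. When Period 2 follows on the next day, the set with the other study insulin goes in before dinner.

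**The concern.** The two SAP sections place the start of Part B exposure at different points. For adverse events generally it is set insertion. For the by-treatment hypoglycaemia tables it is run-in, which comes later. The hours between are on study insulin, and Part B patients are already randomised by then (Day -1 of Period 1, Protocol 7.2), so each event can be attributed to LY900014 or Humalog. The hypoglycaemia tables nevertheless pool them.

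Hypoglycaemia is a named endpoint for the tolerability objective (Protocol Section 4) and an adverse event of special interest (Protocol 9.2). The omitted hours also differ in kind from the included ones. During run-in, the subcutaneous rate is a fixed 0.1 U/hour and glucose is steered to target by intravenous dextrose or regular human insulin. Before run-in, that control has not begun and the pump rate is usually higher. Adding run-in for Part B only suggests the intention was to compare treatments once study insulin was flowing; if so, the window opens too late.

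**Working it through.** The plan gives no figure for this point, so the check sets the timeline against the two SAP rules. Part B, Period 1:

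| Interval | Study-insulin delivery (Protocol 5.1.2.1) | SAP 6.5.1 | SAP 6.5.5 |
|---|---|---|---|
| Arrival (about 17:00) to set insertion | None | Pre-dose | Pooled over treatment |
| Set insertion to run-in (about 21:00 or 22:00) | Current basal rate, or 80% of daily NPH / 24 | Post-dose | Pooled over treatment |
| Run-in | 0.1 U/hour until 2 hours before the MMTT | Post-dose | By treatment, but also inside the pooled pre-MMTT period |
| MMTT, 0 to 300 minutes (or first later insulin dose) | 0.2 U/kg bolus | Post-dose | By treatment |

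The second row is the inconsistency. The third row is the overlap: run-in falls before the MMTT, and no exclusion is written.

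**Hourly rate, as an illustration only.** Inputs from Protocol 6.1: minimum weight 25 kg and total daily dose 0.3 to 1.5 U/kg/day. Assumptions not in the documents: a 70 kg adult, and basal insulin as 40% to 50% of the total daily dose (for patients from MDI, taken as the NPH dose).

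Rate = weight × total daily dose × basal share / 24.

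- 25 kg: 25 × 0.3 × 0.4 / 24 = 0.13 U/hour, up to 25 × 1.5 × 0.5 / 24 = 0.78 U/hour.
- 70 kg: 70 × 0.3 × 0.4 / 24 = 0.35 U/hour, up to 70 × 1.5 × 0.5 / 24 = 2.19 U/hour.
- From MDI (× 0.8): 0.10 to 0.63 U/hour at 25 kg, and 0.28 to 1.75 U/hour at 70 kg.

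Under these assumptions the hourly rate before run-in is at or above the 0.1 U/hour of run-in, and usually several times it.

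**Total amount.** For an 08:00 MMTT, run-in delivers 0.1 × 8 = 0.8 U (22:00 to 06:00) or 0.1 × 9 = 0.9 U (21:00 to 06:00). The matching total before run-in cannot be calculated, because the documents give no clock time for set insertion. In Period 1 the interval is bounded by arrival at about 17:00 and shortened by dinner, so it is at most a few hours and could be close to nil. One hour at 0.13 U/hour would be less than run-in delivers. Only the hourly contrast is firm.

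**The case against.** The strongest reply is that little is at stake. The main Part B exposure is the 0.2 U/kg bolus (0.2 × 25 = 5 U at 25 kg; 0.2 × 70 = 14 U at 70 kg), and it falls in the MMTT window, which is summarised by treatment. The interval is short, the tables are descriptive, and Protocol 10.3.1.1 promises summaries only if event frequency allows. In Period 1 the dinner bolus is the patient's usual insulin, which blurs attribution and could be a reason to pool. The 30- to 60-minute glucose checks are specified for run-in, not for the hours before it. All of this stands, and it limits the size of the point. It does not explain why the same hours are post-dose in SAP 6.5.1 and pooled in SAP 6.5.5.

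A second reply is that run-in was meant to begin at set insertion, or that the pooled category means only the remaining time. The SAP does not define run-in, and the protocol starts it at about 21:00 or 22:00. The remainder reading would remove the overlap but leave the gap. Either reading needs to be written down.

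Four stronger inferences are tempting and not supported:

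- *The events are lost.* They are all listed; severe episodes are reported as SAEs (Protocol 9.4.5.3); and any event also reported as an adverse event would enter the by-treatment tables of SAP 6.5.1.
- *The SAP yields two conflicting treatment-emergent counts.* SAP 6.5.5 tabulates by time window and never classes hypoglycaemia as treatment-emergent.
- *The omitted interval carries several times the study insulin of the included one.* That needs an assumed insertion time and leaves out the MMTT bolus.
- *A Part B patient exposed overnight who stops before the bolus has no follow-up,* because footnote b of the schedule refers to stopping "after receiving study drug on Day 1 of Period 1 and before Day 1 of Period 2". The opening of Protocol Section 8, Section 8.2 and the visit list in Section 5.1.2 already call for follow-up after early discontinuation.

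**Conclusion.** The inconsistency is real and is visible in the text alone. In Part B, the interval from study-insulin set insertion to run-in is post-dose under SAP 6.5.1 but is summarised without regard to treatment under SAP 6.5.5, and the pooled summary overlaps with run-in as written. The practical effect is modest: a short interval of unstated length, descriptive tables, about 36 completing patients, and events that remain in the listings. What is missing is the by-treatment summary for that interval.

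The conclusion assumes that run-in has the protocol's meaning and that set insertion precedes it by a non-trivial time in at least some patients. The second assumption is safest for a consecutive-day Period 2, where the set is in place before dinner. It does not depend on the illustrative basal rates. A rate described as the patient's full basal rate would be accurate only for prior CSII users.

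**What to change.** In SAP 6.5.5, for Part B:

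1. Start the by-treatment hypoglycaemia window at insertion of the study-insulin infusion set, matching SAP 6.5.1.
2. Show set insertion to run-in, run-in, and MMTT as separate by-treatment rows, and define the start and end of run-in.
3. Limit the treatment-independent pre-MMTT row to time before insertion, which also removes the overlap.

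The cost is SAP wording and one extra table row. The insertion time must be available, but SAP 6.5.1 already depends on it. SAP version 2 was approved before Part A was complete (SAP Section 3), and Part B was to start pending review of Part A data (Protocol 5.1), so that version could have carried the change before any Part B data existed.

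There is a small downside: the new row also reflects the dinner bolus. In Period 1 that bolus is the patient's usual insulin. On a consecutive-day Period 2, Protocol 5.1.2.1 has it given through the pump after the reservoir has been filled with study insulin, whereas the Part B Schedule of Activities says prandial insulin is the patient's usual insulin. Footnote the row accordingly, and reconcile those two protocol passages. Footnote b of the schedule needs no change for this point.

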						administration of study drug) and should be consumed within 15 minutes.
Blood Glucose Sampling (MMTT)				-30, -15, 0 (premeal), 10, 20, 30, 40, 50, 60, 70, 80, 90, 100, 110, 120, 135, 150, 165, 180, 195, 210, 225, 240, 300 minutes postmeal		Time is referenced to meal start time, i.e., time 0. Time 0 is collected immediately prior to start of meal consumption.
Insulin Lispro PK Sampling				0, 5, 10, 15, 20, 25, 30, 35, 40, 45, 50, 60, 70, 90, 120, 150, 180, 240, 300, 360, and 420 minutes postdose		Sampling times are relative to the time of study drug treatment administration (t = 0) in each period
Transition to NPH Twice Daily Therapy 7-3 days Prior to Day -1		X				Applicable only to patients using multiple daily injection therapy. Patient can return to pre-study basal insulin following completion of MMTT sampling period per investigator's decision and allowing for transition to NPH prior to next dosing.
Resume Prestudy CSII Rate				X		Applicable only to patients on CSII. CSII with the patient's prestudy insulin will be restarted after

Visits	Screening		Study Periods (Periods 1 and 2)		Follow-up ^a /Early Discontinuation ^b	Comments
	101	Telephone Visit	1 and 2		801	
Day	Within 28 days Prior to Day -1	≥Day -10 ^c	-1 ^d	1	≥14 days After Last Dose of Study Drug	
						completion of assessment period (approximately 420 minutes postdose).
Adverse Events/Hypoglycaemia	X	X	X	X	X	
Concomitant Medications	X	X	X	X	X	
Patient Discharge from Study Site				X		If the next MMTT (Period 2) is scheduled on the next day, the patient may be discharged after the second MMTT (Period 2).

Abbreviations: BP = blood pressure; CSII = continuous subcutaneous insulin infusion; ECG = electrocardiogram; ED = early discontinuation; IWRS = Interactive Web Response System; MMTT = mixed meal tolerance test; NPH = neutral protamine Hagedorn; PK = pharmacokinetics; SC = subcutaneous.

^a Safety follow-up visit should occur at least 14 days after the last dose.

^b Early discontinuation procedures will be performed at least 14 days after a patient stops the study after receiving study drug on Day 1 of Period 1 and before Day 1 of Period 2.

^c This is a telephone visit.

^d In case of dosing on consecutive days, the medical assessments to be conducted on Day -1 of Period 2 may be done on Day 1 of Period 1.

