Patients entering the study on MDI therapy with any basal insulin other than NPH twice daily will transition to NPH twice daily therapy approximately 7 to 3 days prior to Day -1 of Period 1. Transition guidelines, including dosages and timing, will be determined by the investigator and will be based on the needs of individual patient.

On Day -1, the last injection of NPH prior to the MMTT will occur in the morning and will resume only after the completion of the MMTT assessment (~7 hours postdose on Day 1).

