a low carbohydrate snack (<20 g carbohydrate), which does not require an insulin dose, after GD assessments (approximately 300 minutes postdose). Following completion of the assessment period and sample collection (approximately 420 minutes), patients will be offered a meal. For patients who were using MDI therapy, the investigator shall provide guidance on whether they should resume their prestudy basal insulin at the end of Period 1 or continue with NPH depending on the length of time between Period 1 and Period 2. Patients may return to pre-study basal insulin following completion of Period 2 MMTT sampling period with investigator's guidance. For CSII patients, the insulin pump may be resumed at the usual rates and settings with prestudy insulin and bolus mealtime insulin will be administered. A new infusion set may be required.

Patients will be observed following administration of the meal and discharged at the investigator's discretion.

Abbreviations: BG = blood glucose; CSII = continuous subcutaneous insulin infusion; IV = intravenous; MDI = multiple daily injection; MMTT = mixed meal tolerance test; NPH = neutral protamine Hagedorn; PK = pharmacokinetics; RHI = regular human insulin; SC = subcutaneous.

Figure ITSA.2. Inpatient procedure in Part A.

[figure not shown]
Assessment of local tolerability at all injection sites will be performed as specified in the Schedule of Activities (Section 2), including inspection of the injection/catheter site for signs such as oedema, erythema, and rash.

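### Should hypoglycaemia also be tabulated by treatment between 300 minutes after the meal and the return of usual insulin at about 420 minutes?

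*SAP*

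**What the plan says.** SAP 6.5.5 sets two periods in which hypoglycaemia is "summarized by treatment and age group for inpatient during the MMTT and inpatient run-in period (Part B only"). It then defines the meal-test period: it "refers to 0 to 300 minutes post the start time of the meal", or ends at the first insulin dose after the test if that comes sooner. For the rest of the inpatient stay and for the outpatient periods, a "similar summary will be provided by age group independently of randomized treatment assignment". The same section lists every hypoglycaemic event in the study.

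The protocol runs a longer clock for other purposes. Under Protocol 5.1.1 the NPH injections "will resume only after the completion of the MMTT assessment (~7 hours postdose on Day 1"), and 5.1.2 says the same for Part B. In the Schedule of Activities for both parts, patients on pumps restart their own insulin after "completion of assessment period (approximately 420 minutes postdose"). Protocol 5.1.1.1 adds: "Following completion of the assessment period and sample collection (approximately 420 minutes), patients will be offered a meal". Scheduled glucose sampling is shorter; the Part B schedule ends with "195, 210, 225, 240, 300 minutes (postmeal"), and Part A has the same times. From then on a patient may have "a low carbohydrate snack (<20 g carbohydrate), which does not require an insulin dose, after GD assessments (approximately 300 minutes postdose").

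**The concern.** Set side by side, the two clocks seem not to match. The by-treatment table stops at 300 minutes, yet no other insulin is scheduled until about 420 minutes. In between, patients are still on site, the study insulin is the only insulin scheduled to have been given for the test, and the treatment for that period is known. Pooling those two hours with the time after usual insulin and a meal resume mixes events that can be attributed to a treatment with events that cannot.

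Hypoglycaemia is named in the secondary tolerability endpoint (Protocol 4) and is an adverse event of special interest (Protocol 9.2). The study rationale (Protocol 3.1) suggests that a faster-off insulin might reduce postprandial hypoglycaemia. If the table hid a late difference between LY900014 and Humalog, the tolerability account would be incomplete on a point that the product is meant to address.

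**Working it through.** **1. What ends when**

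| Feature | Ends or starts | Source |
|---|---|---|
| By-treatment hypoglycaemia window | ends 300 min after meal start | SAP 6.5.5 |
| Scheduled meal-test glucose samples | last at 300 min after meal start | Protocol 2, both parts |
| No-food rule | ends at about 300 min | Protocol 5.1.1.1, 5.1.2.1, 9.4.6 |
| Longest planned glucose endpoint, ΔAUC(0-5h) | ends at 5 h = 300 min | Protocol 10.3.3.1, SAP 6.4.1 |
| Insulin lispro samples | last at 420 min postdose | Protocol 2, both parts |
| Usual insulin and a meal | start at about 420 min | Protocol 2, 5.1.1, 5.1.1.1, 5.1.2, 5.1.2.1 |

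The cut coincides with the end of the period in which glucose is measured on a schedule and intake is controlled. The table window and the glucose schedule also share the same time origin, the start of the meal.

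**2. Length of the gap.** The table runs from meal start and the 420 minutes run from dosing. With a delay of d minutes from dose to meal, the gap is 420 − (300 + d). The documents give no figure for d, so 0 to 5 minutes is assumed.
- d = 0: 120 minutes; 120/420 = 28.6%.
- d = 5: 115 minutes; 115/420 = 27.4%.

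This is a share of clock time, not of events.

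**3. What is measured in the gap.** Of 24 scheduled glucose samples, 21 fall from 10 to 300 minutes after meal start and 0 fall later. Of 21 insulin lispro samples, 2 fall later (360 and 420 minutes). The documented Level 1 and Level 2 categories each need a glucose value. After 300 minutes they can arise only from an unscheduled check, often prompted by symptoms. Asymptomatic events would be largely unseen, and a snack may prevent others.

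**4. What counts in the gap could show.** The plan gives no event rate for these two hours, so there is no figure of its own to reproduce. For an assumed per-patient risk r under one treatment, the chance of seeing any event among n patients is 1 − (1 − r)^n.

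| r (assumed) | n = 12 (one age group) | n = 36 (all ages) |
|---|---|---|
| 1% | 11.4% | 30.4% |
| 2% | 21.5% | 51.7% |
| 5% | 46.0% | 84.2% |
| 10% | 71.8% | 97.7% |

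Protocol 5.5 describes hypoglycaemia in earlier LY900014 test-meal studies as low, which points to the upper rows. If no event is seen, the one-sided 95% upper bound is 1 − 0.05^(1/12) = 22.1% for 12 patients and 1 − 0.05^(1/36) = 8.0% for 36. A further row would add 2 treatments × 3 age groups × 2 parts = 12 cells for each hypoglycaemia category, most of them probably zero.

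**5. Who would be counted.** Attribution to study insulin alone requires leaving out patient-periods in which intravenous regular human insulin was given earlier for high glucose. That selects on a post-dose event whose frequency may itself differ by treatment.

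**6. What is lost under the plan as written.** All events are recorded in the eCRF and severe ones are reported as serious adverse events (Protocol 9.4.5.3). SAP 6.5.5 lists all hypoglycaemia, and SAP 6.5.1 tabulates serious events. SAP 6.5.1 also summarises treatment-emergent adverse events by treatment and age group, with no 300-minute limit. Study-drug dose times are recorded (Protocol 7.2.1), and the 300-minute rule already needs event times, so an event at, say, 350 minutes can be traced to its treatment. Protocol 10.3.1.1 promises descriptive summaries of hypoglycaemia only if frequency allows, and SAP 6.5.5 meets that.

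**The case for a change.** The best case for adding the window rests on the SAP's own logic. It ends attribution at the first insulin after the test, and it reports the Part B run-in by treatment, when study insulin is already in the pump. On that logic attribution could continue to about 420 minutes. Exposure is analysed by treatment over seven hours through AUC(0-7h), and Protocol 5.1.1 itself places the end of the meal-test assessment at about seven hours. The data exist, and a separate descriptive row would leave the main table unchanged.

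The timing facts in this argument are right, and the pooled after-test category does combine two situations. The step from there to a defect fails. Lispro is sampled to 420 minutes, but glucose, which defines most of the hypoglycaemia categories, is not. The SAP gives its own definition of the meal-test period, so the looser use of the term in Protocol 5.1.1 causes no ambiguity. The new row would rest on ad hoc detection, optional carbohydrate, selected patient-periods and very small counts. A difference between treatments there could mislead as easily as inform, and experienced statisticians could reasonably choose either way.

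One loose end remains: SAP 6.5.1 does not say whether events from the separate hypoglycaemia module enter the treatment-emergent tables. That is a detail of table specification. The listing and the serious adverse event table cover these events in either case.

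**Conclusion.** The concern does not hold. The 300-minute limit is tied to the end of scheduled glucose sampling, controlled intake and the glucose endpoints, and the SAP states it clearly. About 115 to 120 minutes of post-dose time are left out of the by-treatment hypoglycaemia table, but no event is left out of the reporting. The difference is one of presentation. It touches neither sample size, power nor alpha, and no pharmacokinetic, glucodynamic or safety conclusion changes.

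This rests on a dose-to-meal delay of 0 to 5 minutes, which is assumed, and on the complete listing of events that SAP 6.5.5 promises. The event rates above are illustrative; the conclusion does not depend on any one of them, nor on whether the treatment-emergent tables include hypoglycaemia-module events.
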